6.3 End of Treatment Study Procedures

At the end of treatment, patients will be assessed with a history and adverse event assessment.

Patients who receive maintenance therapy and achieve a CR will be assessed at the time of disease progression with a history, adverse event assessment, and bone marrow biopsy to confirm progression.

6.4 **Post-treatment/Follow-Up**

Patients will be followed every three months for one year after treatment ends for evidence of late toxicity. Follow up visits will either occur as part of routine clinical visits (standard of care) or through review of the patient medical record. Patients who were ineligible for transplant at study entry but achieve a CR and thus become transplant eligible will be followed.

6.5 Withdrawal Visit/Discontinuation of Therapy

If a patient withdraws early or the investigator terminates a patient's participation the following should still be offered to the patient:

• Recording of adverse events

- Recording of physical examination
- Recording of compliance with palbociclib and dexamethasone

7 Study Procedures and Evaluations

7.1 Study Procedures/Evaluations

At enrollment/baseline, each patient will have a medical history. This will include a review of the patient's medical record. A medication history will be obtained. Patients will also undergo a physical exam (including neurological exam), vital signs, and performance status assessment.

7.2 Laboratory Procedures/Evaluations

7.2.1 Clinical Laboratory Evaluations

Laboratory studies will include a CBC with differential, metabolic panel (creatinine, BUN, glucose), magnesium, phosphate, urate, liver function tests (bilirubin, SGOT (AST), SGPT (ALT), alkaline phosphatase), and a serum or urine pregnancy test, if applicable.

7.2.2 Special Assays or Procedures

Plasma levels of palbociclib for will be determined by a validated assay performed at PPD in Richmond, VA. See Appendix C for full instructions on sample storage, handling, and processing for PK/PD analysis. Palbociclib levels will be obtained **within 1 hour prior** to dosing with dexamethasone and palbociclib on days +1 and +8 of induction.

For analyses of molecular markers of palbociclib and dexamethasone response, we will perform western blots of phospho-RB (using antibodies that recognize CDK4/6 phosphorylation sites on RB) and FOXM1 (CDK4/6 substrate which is stabilized by phosphorylation) on lysates from peripheral blood or bone marrow CD19+ cells (obtained by FACS sorting). We will also assess levels of p21, cyclin E, and CDK2 as markers of cell cycle activity.

As markers of Dexamethasone response, we will assess MYB and BCL2 levels in pre-treatment and post-treatment (palbociclib and dexamethasone combination) CD19+ peripheral blood or bone marrow cells.

For analyses of additional markers of drug response, RNA will be isolated from pre-treatment and post-treatment CD19+ cells and used for gene expression profiles (microarray or RNA-Seq).

7.2.3 Specimen Preparation, Handling, and Storage

Details regarding specimen preparation, handling, and storage for palbociclib PK analysis can be found in Appendix C.

Details regarding specimen preparation, handling, and storage for PD analyses can be found in Appendix C.

7.2.4 Specimen Shipment

Details regarding specimen shipping for palbociclib PK analysis can be found in Appendix C.

8 Evaluation of Safety

Patients will be followed for toxicity for one year after the last dose of the study drugs, or until resolution of serious adverse events, if one is noted.

8.1 **Specification of Safety Parameters**

8.1.1 Unanticipated Problems

Unanticipated problems (UAPs) include, in general, any incident, experience, or outcome that meets the following criteria:

 unexpected in terms of nature, severity, or frequency given (a) the research procedures that are described in the protocol-related documents, such as the IRB-approved research protocol and informed consent document; and (b) the characteristics of the participant population being studied;

UAPs are considered to pose risk to participants or others when they suggest that the research places participants or others at a greater risk of harm (including physical, psychological, economic, or social harm) than was previously known or recognized.

These problems are reported to the IRB and are different from, but linked to, regulatory reporting required by the FDA.

8.1.2 Adverse Events

An adverse event is any untoward or unfavorable medical occurrence in a human participant, including any abnormal sign (for example, abnormal physical exam or laboratory finding), symptom, or disease, temporally associated with the participant's participation in the research, whether or not considered related to the participant's participation in the research.

8.1.3 Serious Adverse Events

A serious adverse event (SAE) is one that meets one or more of the following criteria:

- Results in death
- Is life-threatening (places the participant at immediate risk of death from the event as it occurred)
- Is disabling or incapacitating
- Results in inpatient hospitalization or prolongation of existing hospitalization

- Results in a persistent or significant disability or incapacity
- Results in a congenital anomaly or birth defect
- An important medical event that may not result in death, be life threatening, or require hospitalization may be considered an SAE when, based upon appropriate medical judgment, the event may jeopardize the participant or may require intervention to prevent one of the outcomes listed in this definition.

8.2 Safety Assessment and Follow-Up

Adverse event reporting will begin after study treatment, unless the AE/SAE is caused by a study specific screening procedure, and continue until 30 days (for all AEs and SAEs) after the last dose of study treatment or initiation of a new anti-cancer therapy. At each study visit, the investigator (or designee) will inquire about the occurrence of AE/SAEs since the last visit. Events will be followed for outcome information until resolution or stabilization.

8.3 **Recording Adverse Events**

The following subsections detail what information must be documented for each adverse event occurring during the time period specified in Section 8.2 Safety Assessment and Follow-Up. See section 8.4 for reporting details.

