3.1 Number of Participants

A minimum of 4 and a maximum of 18 patients will be enrolled.

3.2 **Duration of Therapy**

Initially, patients will receive single agent palbociclib during induction for

pharmacokinetic/pharmacodynamics (PK/PD) evaluation followed by combination induction therapy with palbociclib and dexamethasone. Patients who do not achieve a CR, CRi, PR, or SD after induction therapy will be taken off the study. Patients who achieve a CR, CRi, PR, or SD will receive on palbociclib and dexamethasone maintenance until disease progression or dose limiting toxicity. Patients who are transplant ineligible at study entry but achieve a CR and thus become transplant eligible may come off study and proceed to transplant. Patients who achieve stable disease, but not a CR, will be re-consented after 6 cycles to continue on the study.

3.3 **Duration of Follow Up**

Patients will be followed for late toxicities for 1 year following the discontinuation of therapy.

3.4 **Study Timeline**

3.4.1 **Primary Completion**

We anticipate that accrual will be complete within 42 months.

3.4.2 **Study Completion**

The study will be complete 2 years after the enrollment of the last patient (66 months total study duration).

4 Study Enrollment and Withdrawal

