Definite	and and and Hours) IRB IRB IRB Annual Annual Annual Review Review		Phase II - 5 working days	Hours)	Review	(Death: 24 Hours)		

8.4.3 **Reporting to Funding Sponsor**

SAEs, as well as all other safety information at the end of the study or as requested by the funding sponsor, will be reported to Pfizer within 24 hours of occurrence by faxing the Pfizer SAE Event Form to the Pfizer US Clinical Trial Department at [name] (Appendix E).

Serious adverse events and all other safety information as defined below will be collected from day -7 of the lead-in period with palbociclib until 28 days after discontinuation. Safety Information is defined as any information from any source containing information such as:

- Adverse event or suspicion thereof
- Lack of efficacy
- Overdose/incorrect dosage (accidental or intentional)
- Abuse/misuse (e.g., patients sharing medication) even without resulting adverse reaction
- Accidental exposure (e.g., child takes parents medication)
- Medication error
- Withdrawal reactions
- Disease progression/exacerbation of existing disease
- Drug-drug/Drug-food interaction
- Reports of unexpected benefit
- Exposure to drug during pregnancy, where the embryo or fetus may have been exposed to medicinal products (either through maternal exposure or transmission of a medicinal product via semen following paternal exposure).
- Exposure to drug during lactation (including uneventful)
- Suspected counterfeit product
- Suspected transfer of infectious disease/agent by the medicinal product concerned.
- Product complaint report (any deficiencies related to the identity, quality, labeling, durability, reliability, efficacy, performance of a medicinal product, suspected counterfeit product)
- Pediatric use (if not an approved use)
- Occupational exposure
- Off-label use (if not part of the study design)

8.4.4 **Reporting to FDA**

For studies conducted under an Investigator IND in the US, any event that is both serious and unexpected must be reported to the Food and Drug Administration (FDA) as soon as possible and no later than 7 days (for a death or life-threatening event) or 15 days (for all other SAEs) after the investigator's or institution's initial receipt of the information. Pfizer Inc. will be provided with a simultaneous copy of all adverse events filed with the FDA.

SAEs will be reported on MedWatch Form 3500A, which can be accessed at: http://www.accessdata.fda.gov/scripts/medwatch/.

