** Optimal therapy for vomiting and diarrhea should be based on institutional guidelines with consideration of the prohibited medications listed in these protocol guidelines.

The design is constructed to reduce the chance of escalating the dose when the probability of DLT is high, and increase the chance of escalating the dose when the probability of DLT is low. The maximum tolerated dose (MTD) is defined as the highest dose level where a DLT occurs in at most one out of six patients treated. The escalation scheme is as follows:

(1) If none of the initial three patients in a cohort experiences a DLT, then a new cohort of three patients will be treated at the next higher dose level.

(2) If one of the three patients in a cohort experiences a DLT, then up to three additional patients will be treated at the same dose. Escalation will continue if only one of six patients experiences DLT.

(3) If two or more patients in a cohort experience DLT, then the MTD will have been exceeded, and no further dose escalation will occur. The previous dose level will be considered the MTD.

(4) If only three patients were treated at a dose level under consideration as the MTD, then up to three additional patients will be accrued. If no more than one of the six patients at that dose level experience a DLT, then that dose level will be confirmed as the MTD. If two or more patients in that cohort experience DLT, then the previous dose level will be studied in the same fashion.

The MTD is defined as the highest dose studied for which the observed incidence of DLT is less than 33%. Frequencies of toxicities will be tabulated according to the NCI Common Toxicity Criteria. Patients will be continued to be followed for one year for evidence of late toxicity.

Table 1.1 below gives the probabilities of dose escalation based on true DLT risk in the 3+3 design.

True DLT rate										
		10%	20%	30%	40%	50%	60%	70%	80%	90%
Probability c escalation	of	0.91	0.71	0.49	0.31	0.17	0.08	0.03	0.01	0.001

All patients treated with at least one dose will be included in the safety analysis.

Response criteria for the study are defined as follows:

Response Criteria Complete Remission (CR) No lymphoblasts in the bone marrow Absolute neutrophil count ≥0.75 x10⁹/L Platelet count ≥75 x 10⁹ /L

Complete Remission with Incomplete Hematologic Recovery (CRi)

<5% lymphoblasts in the bone marrow

Partial Remission (PR)

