- 6. All AEs will be followed until resolution. Patients will be monitored for AEs for 30 daysafter the end of therapy or until initiation of a new anti-cancer therapy.
- 7. Serum chemistry and electrolytes labs should include: creatinine, BUN, glucose, magnesium, phosphate, and urate. Liver function labs should include: bilirubin, SGOT (AST), SGPT (ALT), alkaline phosphatase.
- 8. Patients will be followed for disease status until relapse/progression
- 9. Correlative studies will be performed by the [name] laboratory on peripheral blood or bone marrow.
- 10. Labs and bone marrow biopsy/aspirate may be performed ±2 days from the desired study day.
- 11. Patients who remain on maintenance for >6 months may have labs checked monthly.

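### One year of late-toxicity follow-up is promised, but the adverse event rules require recording only to 30 days or new anti-cancer therapy, so late-onset toxicity has no defined route into the data

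*Combined protocol and SAP*

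**What the plan says.** Four places promise a year. Section 3.3 sets one year of late-toxicity follow-up after therapy stops. Section 6.4 gives the schedule, every three months for a year, and lets each contact be a routine clinic visit or a chart review. The opening of Section 8 says: "Patients will be followed for toxicity for one year after the last dose of the study drugs", or until serious events resolve. Section 11.2, straight after the sentence on tabulating toxicity frequencies, says: "Patients will be continued to be followed for one year for evidence of late toxicity".

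Three places set a much shorter window for the data themselves:

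- Section 8.2 has AE and SAE reporting "continue until 30 days (for all AEs and SAEs) after the last dose of study treatment or initiation of a new anti-cancer therapy".
- Section 8.3 lists what must be documented, including relationship, expectedness and severity, for "each adverse event occurring during the time period specified in Section 8.2 Safety Assessment and Follow-Up".
- Appendix A marks an AE assessment in the follow-up column, but footnote 6 limits monitoring to 30 days after therapy ends or until new anti-cancer therapy. The same footnote says "All AEs will be followed until resolution".

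On the timeline, Section 3.4.2 states: "The study will be complete 2 years after the enrollment of the last patient". Section 3 lets maintenance run until progression, dose limiting toxicity or an alternative therapy, with no maximum duration.

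**The concern.** Safety and tolerability of the combination is a primary objective (Section 2.1.1). The one-year commitment appears in the safety chapter and in the analysis plan, so a reader of the final report will expect late toxicity to have been looked for systematically. The operational rules do not require that. Study staff who follow 8.2, 8.3 and footnote 6 to the letter need not record a toxicity that first appears at month 4. Staff who follow 3.3, 6.4 and 11.2 would look for it, but they have no rule on how to grade, attribute or enter it. Both would be compliant, and their data would differ.

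The risk is one of interpretation. If the late-toxicity section of the report is empty, nobody can tell whether no late toxicity occurred or whether none had to be written down. In a study this small, even one or two unrecorded related events would change the description of tolerability.

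**Working it through.** The plan gives no figure to reproduce here. The check is a comparison of the stated windows, with simple day counts.

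**Inputs**
- Promised follow-up: 1 year after treatment, taken as 365 days (3.3, 6.4, Section 8 opening, 11.2).
- Contacts: every three months (6.4), taken as equally spaced quarters.
- AE window: 30 days after the last dose, or start of new anti-cancer therapy (8.2; carried into 8.3; repeated in Appendix A footnote 6).
- Accrual 42 months; total study duration 66 months (3.4.1, 3.4.2).

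**Step 1: share of the promised year inside the AE window.** 30 / 365 = 8.2%. The remainder is 365 − 30 = 335 days, and 335 / 365 = 91.8%.

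**Step 2: position of the quarterly contacts.** 365 × k/4 for k = 1 to 4 gives about days 91, 182, 274 and 365. The earliest falls 91 − 30 = 61 days after the window closes, so none of the four lies inside it.

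**Step 3: what is required for each kind of event**

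| Event | Followed up? | Recording, grading and attribution required? |
|---|---|---|
| Onset on treatment, including long maintenance | Yes | Yes (8.2, 8.3) |
| Onset within 30 days of last dose, no new therapy | Yes, to resolution or stabilization | Yes (8.2, 8.3) |
| Onset from day 31 to one year | Yes, in principle (3.3, 6.4, 8, 11.2) | No rule |
| Onset after new anti-cancer therapy | Yes, in principle | No rule once the new-therapy limit applies |

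Section 11.2 does not fill the gap. It sets no cut-off for tabulating toxicities, but it also does not say which late events are tabulated, or how events before and after new therapy are separated. Section 8.2 does not say whether the 30-day and new-therapy limits combine as whichever comes first. If they do, new therapy before day 30 shortens the window further.

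**Step 4: study closure (secondary).** 66 − 42 = 24 months from last enrolment to completion. Reserving 12 months for follow-up leaves 24 − 12 = 12 months between enrolment and last dose for the last-enrolled patient. If that patient's treatment runs beyond this, the promised year cannot be completed before the study closes.

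**The case against.** The strongest reply is that nothing in the documents excludes late toxicity. Much of it stands:

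- Section 8.3 says what must be documented inside the window. It does not forbid recording later events.
- Section 11.2 tabulates toxicities without a cut-off.
- Events that begin inside the window are followed to resolution or stabilization, and toxicity arising during long maintenance is on treatment and so captured.
- Appendix A also schedules medical history and concomitant medication review at follow-up.
- FDA reporting of serious unexpected events (8.4.4) and IRB reporting of grade 5 events (8.4.1.3) carry no 30-day limit.

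A reader might therefore infer from 8.2 and 8.3 that late toxicity can never reach the safety data, or that sites will record nothing after the first quarterly contact. The documents do not support either statement. What they support is that recording late-onset toxicity is not required and the method is undefined.

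Three further inferences should also be resisted. First, 92% is a share of calendar days, not of toxicity lost; the documents give no rate of late events, and not every patient will be observable for a year. Second, one might assume that most patients start another therapy quickly. Section 3 does list availability of an alternative therapy as a reason to end maintenance, but no figure says how often or how soon. Third, Section 8.4.3 collects safety information for the funder "until 28 days after discontinuation". That is a separate reporting duty lying wholly inside the 30 days, so it does not contradict 8.2.

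It may also be said that 8.2 requires AE inquiry at every study visit, which could include follow-up. But the same paragraph sets the 30-day limit, footnote 6 applies it to the follow-up column, and 6.4 allows follow-up by chart review alone.

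**Conclusion.** The point holds as a conflict between stated rules. Four sections promise a year of toxicity follow-up, while the three places that govern data capture stop at 30 days or new anti-cancer therapy. Toxicity with later onset has no required recording, grading, attribution or tabulation. The uncovered part is at least 335 of 365 days and includes all four quarterly contacts, taking a year as 365 days and equal quarters. The number of events that would be missed cannot be derived from the documents.

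The consequence is possible incompleteness and the risk that an empty late-toxicity result is misread as absence of toxicity. Dose decisions are not affected: the DLT evaluation period is 35 days from the start of the lead-in (6.2.1), and the MTD rests on it. The study-closure point is conditional, arising only for a patient enrolled at or near the end of accrual and treated for more than about 12 months. The issue bears on a primary objective and is cheap to correct, so the sponsor should correct it.

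**What to change.** - **Sections 8.2 and 8.3 and Appendix A footnote 6:** keep the 30-day window for all AEs, and state how it combines with the new-therapy limit. Add that, from then to 12 months after the last dose, any event (SAEs included) judged at least possibly related to study treatment is recorded, graded and attributed at the existing three-monthly visit or chart review, including after new anti-cancer therapy. Capture the start date of that therapy on the CRF.
- **Section 11.2:** state that these late events are tabulated separately from events in the 30-day window, split into before and after the start of new therapy, and report how many patients were under observation at each quarterly contact. An empty cell can then be interpreted.
- **Section 3.4.2 (secondary):** either extend completion for patients still within their follow-up year when the 24 months end, or state that their follow-up is truncated at closure.

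The cost is protocol wording and a few more CRF entries; the quarterly contacts are already in the plan. Attribution will be harder once another therapy has started, which is why its start date and the split table are needed. Choosing to extend completion could take the study past 66 months if a late-enrolled patient stays on long maintenance.

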8.3.1 Relationship to Study Intervention

The relationship to study intervention or study participation must be assessed and documented for all adverse events. Evaluation of relatedness must consider etiologies such as natural history of the underlying disease, concurrent illness, concomitant therapy, study-related procedures, accidents, and other external factors.

The following guidelines are used to assess relationship of an event to study intervention:

- 1. Related (Possible, Probable, Definite)
 - a. The event is known to occur with the study intervention.
 - b. There is a temporal relationship between the intervention and event onset.
 - c. The event abates when the intervention is discontinued.
 - d. The event reappears upon a re-challenge with the intervention.
- 2. Not Related (Unlikely, Not Related)
 - a. There is no temporal relationship between the intervention and event onset.
 - b. An alternate etiology has been established.

8.3.2 **Expectedness**

The PI is responsible for determining whether an AE is expected or unexpected. An AE will be considered unexpected if the nature, severity, or frequency of the event is not consistent with the risk information previously described for the intervention. Risk information to assess expectedness can be obtained from preclinical studies, the investigator's brochure, published medical literature, the protocol, or the informed consent document.

8.3.3 Severity of Event

Adverse events will be graded for severity according to the Common Terminology Criteria for Adverse Events (CTCAE) version 5.0.

